4. CASE DEFINITIONS

Stools will be graded as follows:

- Grade 1: firm formed;
- Grade 2: soft formed;
- Grade 3: viscous opaque liquid or semi-liquid which assumes the shape of the bowl;
- Grade 4: watery opaque liquid;
- Grade 5: clear watery or mucoid liquid.

4.1. Diarrhea

For the purpose of this study, diarrhea is defined as:

- Moderate diarrhea: 4 to 5 loose or watery (Grade 3 to 5) stools or 400 to 800 grams of Grade 3 to 5 stools within 24 hours.
- Severe diarrhea: 6 or more loose or watery (Grade 3 to 5) stools or > 800 grams of Grades 3 to 5 stools within 24 hours or required medical intervention. In case of severe diarrhea, medical intervention is defined as intravenous (IV) fluids administration or anticipation of antibiotic treatment before the 5th day after challenge.
- More severe diarrhea: 10 or more loose or watery (Grade 3 to 5) stools or ≥ 1000 grams of Grade 3 to 5 stools within 24 hours.

205626 (S SONNEI MONO GMMA SBVGH-003 [H03_03TP])
Protocol Amendment 6 Final

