- They have diarrhea (any severity stool Grade 3 or higher) and two or more of the following symptoms: severe abdominal pain/cramps, severe nausea, severe headache, severe myalgia, severe arthralgia, gross blood in ≥ 2 stools, any fever (≥ 38.0°C measured orally), or any vomiting.
- They experience unexpectedly severe events such as hypotension (disproportionate to volume loss), renal dysfunction, or altered mental state (e.g. somnolence) at the discretion of the investigators.
- A study physician determines early treatment is warranted for other reasons.

A subject receiving early antibiotic treatment will still remain on the unit until the planned day of discharge (the 9th day of inpatient stay: Day 65). On that day, if a subject is clinically well and has had at least 2 negative stool cultures, collected at least 6 hours apart, for *S. sonnei*, s/he will be discharged. A subject that, on the planned day of discharge, still had S. *sonnei* isolated from the Day 64 stools will be asked to remain in the unit until s/he is no longer shedding. A subject still shedding 48 hours after initiation of ciprofloxacin will be switched to a Septra DS (1 tablet twice a day for five days). If a subject is still positive 48 hours after the second-line antibiotic is administered, a culture and antibiotic sensitivity test will be obtained and therapy initiated based on sensitivity results. If a subject has two consecutive negative stool samples and is eligible to be discharged from the inpatient stay but did not finish his treatment course, s/he can be given the remaining doses to complete at home.

Following discharge, subjects will return at 28 days (Visit 6), 56 days (Visit 7) and 6 months (Visit 8) after challenge for outpatient clinical assessment. During these visits, clinical assessment will be done to assess their general health status and find out about the occurrence of AESI, any AE and SAE.

[figure not shown]
Subjects will be advised at the time of their discharge to contact the study staff/doctor if they feel unwell. The subjects will be followed up until 6 months after the challenge. At the last study visit, at 6 months after challenge, the subject will be reviewed for the occurrence of any AESI and the site staff will ensure all AEs are resolved.

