4.3. Shigellosis

For the primary and secondary objectives in the challenge phase of the study, the protocol primary case definition for shigellosis is:

• Shedding of *S. sonnei* 53G accompanied by moderate or severe diarrhea OR shedding with an oral temperature of ≥ 38.5 °C).

For the secondary objectives in the challenge phase of the study, 2 definitions of shigellosis are used:

- 1. CHIM working group case definition for shigellosis as defined by any one of the three following possible endpoints:
 - Severe diarrhea defined as [≥6 loose stools in 24 hours] OR [>800 grams loose stools in 24 hours]
 - Moderate diarrhea defined as [4-5 loose stools in 24 hours OR 400-800 grams loose stools in 24 hours] AND [oral temperature ≥38.0°C OR ≥1 moderate constitutional/enteric symptom OR ≥2 episodes of vomiting in 24 hours]
 - Dysentery defined as [≥2 loose stools with gross blood (hemoccult positive) in 24 hours] AND [oral temperature ≥38.0°C OR ≥1 moderate constitutional/enteric symptom OR ≥2 episodes of vomiting in 24 hours].
- 2. Shigellosis as defined by any one of the three following possible endpoints:
 - Severe diarrhea defined as [≥6 loose stools in 24 hours OR >800 grams loose stools in 24 hours]
 - Moderate diarrhea defined as [4-5 loose stools in 24 hours OR 400-800 grams loose stools in 24 hours] AND [oral temperature ≥38.0°C OR ≥1 moderate constitutional/enteric symptom].
 - Dysentery defined as [≥2 loose stools with gross blood (hemoccult positive) in 24 hours] AND [≥1 reportable constitutional/enteric symptom].

For the secondary objectives in the challenge phase of the study, more severe shigellosis is defined by any one of the two following possible endpoints:

- Moderate OR severe diarrhea [≥4 loose stools in 24 hours OR ≥400 grams loose stools in 24 hours] AND [oral temperature ≥38.0°C OR ≥1 severe constitutional/enteric symptom].
- Dysentery defined as [≥2 loose stools with gross blood (hemoccult positive) in 24 hours] AND [oral temperature ≥38.0°C OR ≥1 severe constitutional/enteric symptom]. (Amended: 23 July 2019)

205626 (S SONNEI MONO GMMA SBVGH-003 [H03_03TP])
Protocol Amendment 6 Final

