11.2. Secondary endpoints

Efficacy

VE, in subjects receiving the 1790GAHB vaccine vs. placebo, will be also measured during inpatient stay (Day 57 to Day 64) against:

- Rate of shigellosis *as defined by* the CHIM working group case definition for shigellosis occurring within a period starting with challenge visit and lasting until the end of the inpatient stay, in all subjects. (*Amended: 23 July 2019*)
- Rate of shigellosis, as defined by: severe diarrhea OR moderate diarrhea with fever or with one or more moderate constitutional/enteric symptom OR dysentery [[≥2 loose stools with gross blood (hemoccult positive) in 24 hours] AND [≥1 reportable constitutional/enteric symptom]].
- Rate of more severe shigellosis as defined by: severe or moderate diarrhea with fever or with one or more severe constitutional/enteric symptom OR dysentery [[≥2 loose stools with gross blood (hemoccult positive) in 24 hours] AND [*oral temperature* ≥38.0°C OR ≥1 severe constitutional/enteric symptom]]. (Amended: 23 July 2019)
- Shedding of *S. sonnei* strain 53G.
 - Shedding of *S. sonnei* strain 53G is defined as positivity of at least one stool sample either by culture or qPCR or both.
- Severe diarrhea
- More severe diarrhea.
- Dysentery.

205626 (S SONNEI MONO GMMA SBVGH-003 [H03_03TP])
Protocol Amendment 6 Final

- Weight of all grade 3-5 stools.
- Total number of all grade 3-5 stools.
- Confirmed S. sonnei 53G shedding AND moderate or severe diarrhea OR dysentery OR presence of oral temperature ≥ 38.5 °C OR presence of one or more severe intestinal symptoms (abdominal pain, cramping, nausea, vomiting, gas, anorexia).
- Disease not fulfilling the protocol primary case definition for shigellosis associated or not with mild to moderate symptoms including: passing loose stool (not meeting the protocol definition of moderate or severe diarrhea), abdominal pain, abdominal cramps, gas, anorexia, nausea, headache, myalgia, malaise, arthralgia, fever, vomiting and IV fluid administration.
- Time to onset of shigellosis after challenge, according to the protocol primary case definition.

Safety

Solicited adverse events

• Occurrence of each solicited local and systemic adverse event within 7 days after each vaccination.

Unsolicited adverse events

• Occurrence of unsolicited AEs within 28 days after vaccination and after challenge, according to Medical Dictionary for Regulatory Activities (MedDRA) classification.

Serious adverse events

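### Read literally, Section 4.1 lets IV fluids or early antibiotics alone turn a shedding subject into a primary case; tie that route to treatment given for diarrhea and test the result without it

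*Protocol*

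**What the plan says.** Section 4.1 gives the lower grade these thresholds: "Moderate diarrhea: 4 to 5 loose or watery (Grade 3 to 5) stools or 400 to 800 grams of Grade 3 to 5 stools", counted over one day. To be severe, it takes 6 or more such stools, or more than 800 g of Grade 3 to 5 "stools within 24 hours or required medical intervention". The next sentence states that "medical intervention is defined as intravenous (IV) fluids administration or anticipation of antibiotic treatment before the 5th day after challenge". Table 20 (Section 9.3.3.2.1) has the same alternative in Grade 3 diarrhea.

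The primary case definition in Section 4.3 is shedding "accompanied by moderate or severe diarrhea OR shedding with an oral temperature of" 38.5°C or more. It gives no stool threshold of its own. The two secondary shigellosis definitions in the same section do. The first, from the CHIM working group, reads "Severe diarrhea defined as [≥6 loose stools in 24 hours] OR [>800 grams loose stools in 24 hours", and neither has an intervention route.

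Section 3.2 permits antibiotics before the 5th day in three situations. The first begins "They have diarrhea (any severity stool Grade 3 or higher" and adds two or more listed symptoms, among them any temperature of 38.0°C or above and any vomiting. The second is unexpectedly severe events such as hypotension or altered mental state. The third is "A study physician determines early treatment is warranted for other reasons". Section 9.1.3.3 lists the findings that lead a physician to consider IV fluids. None of them is a stool count or a temperature.

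Section 11.2 has a secondary endpoint for disease that does not fulfil the primary definition. Its list of features ends with "vomiting and IV fluid administration".

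**The concern.** The primary endpoint carries the trial's only success criterion (Section 2.1: lower 90% limit of VE above zero). A case should therefore follow from illness and shedding, and two subjects with the same illness should be classified the same way.

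Take two shedding subjects, each with 2 to 3 loose stools under 400 g, a temperature of 38.0°C and one episode of vomiting. Both meet the first early-antibiotic condition, but Section 3.2 says only that such subjects may be treated. The one who is treated is a primary case under Section 4.1 and the other is not. The difference lies in a treatment decision, which holds whichever way VE moves.

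Two further points follow. Severe diarrhea selects different subjects depending on the endpoint. And a shedding subject given IV fluids is already a primary case under Section 4.1, so for that subject the Section 11.2 list conflicts with it.

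**Working it through.** **The plan's own figure (Section 11.4).** Inputs: true VE 70%, one-sided alpha 5%, 80% power, placebo attack rate 58%, 22% non-evaluable.

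- Share of cases in the vaccine arm: 0.5 under no effect, and 0.3/1.3 = 0.2308 at VE 70%.
- With 21 cases, the exact binomial rule rejects at 6 or fewer vaccine cases: alpha 0.0392, power 0.808.
- Evaluable per arm: 21/(0.58 × 1.3) = 27.9, so 28. Recruited per arm: 28/0.78 = 35.9, so 36, or 72 in total.

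The stated sample size reproduces. It does not reveal how the 58% was counted.

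**Common basis for the scenarios.** 28 evaluable per arm and true attack rates of 58% and 0.3 × 58% = 17.4%. Power is by full enumeration of two binomials. Success means that the upper 90% limit of the log risk ratio is below 0; with no vaccine cases, at least 5 placebo cases are required. Without the intervention route, power is 93.5%. This is a different calculation from the plan's one-proportion figure, so scenarios should be compared with 93.5%, not with 80%.

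**Scenario A, cases unrelated to vaccine.** Assumption: a share q of otherwise non-cases enters through the route, equal in both arms. The protocol gives no value for q. The observed rate in each arm is p + q(1 − p), and VE is 1 minus the ratio.

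| q | Placebo | Vaccine | VE | Power |
|---|---|---|---|---|
| 0 | 0.580 | 0.174 | 70.0% | 93.5% |
| 2% | 0.588 | 0.191 | 67.6% | 92.1% |
| 5% | 0.601 | 0.215 | 64.2% | 90.0% |
| 10% | 0.622 | 0.257 | 58.7% | 86.1% |
| 15% | 0.643 | 0.298 | 53.7% | 81.8% |

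The vaccine arm has more non-cases to convert. At q = 10% it gains 28 × 0.826 × 0.10 = 2.3 cases, against 28 × 0.42 × 0.10 = 1.2 in the placebo arm.

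**Scenario B, cases prevented like other shigellosis.** The placebo rates are those of Scenario A and the vaccine rate is 0.3 times the placebo rate. VE stays at 70%, and power rises to 94.0% at q = 2% and 96.6% at q = 15%.

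**Scenario C, route removed.** Assumption: a share of true cases is treated before reaching a stool or temperature threshold and is lost equally in both arms. VE stays at 70%.

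| Share lost | Expected cases | Power |
|---|---|---|
| 0 | 21.1 | 93.5% |
| 10% | 19.0 | 89.5% |
| 20% | 16.9 | 84.4% |
| 30% | 14.8 | 77.9% |

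**The case against.** **A contradiction with the primary definition.** A reader might infer that Section 4.1 contradicts the primary definition in Section 4.3. It does not: that definition gives no threshold and depends on Section 4.1. The stool-only wording belongs to the secondary definitions, and the protocol varies component meanings by endpoint on purpose, as it does for dysentery in Section 4.2. The objection stands on this point. What remains is one label with two meanings.

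**Passages that cannot all hold.** Every primary case needs shedding, so IV fluids in a non-shedder fit the Section 11.2 list. The conflict is confined to shedders.

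**The narrower reading.** The limb sits inside a definition of diarrhea, so it may be meant only for intervention that diarrhea required. That is a fair reading, but the text does not say so. If the limb applied only once diarrhea was already severe by count or weight, it would classify nobody. The amendment history points to a stand-alone route: Amendment 3 appears to have changed the Table 20 wording from *and* to *or*. Amendment 4 revised more severe diarrhea for consistency with the shigellosis definition, and that category now has no intervention limb.

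**Dilution.** A reader might also infer that the limb dilutes VE. The documents do not support that. They give no q, treatment decisions are observer-blind, and a shedding subject with diarrhea and two of the listed symptoms may well have true shigellosis. Section 11.4 says that the 58% is for this study's primary definition. If it already includes the limb, adding q on top counts those cases twice.

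**Removing the limb.** Section 1.3.1 says that an effective antibiotic reduces or ends symptoms within 24 hours. Early treatment can therefore stop a true case before it reaches a threshold, and counting such a subject as a case is defensible. Scenario C shows the cost of dropping the limb. This is a good reason to keep it in the primary definition.

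**Conclusion.** The point holds as a defect of specification. On the literal text, a shedding subject below 4 loose stools, 400 g and 38.5°C can become a primary case solely through IV fluids or early antibiotics, including treatment for a non-diarrheal event or at a physician's discretion. The same term is stool-only in the secondary shigellosis definitions, and the IV-fluid item in Section 11.2 conflicts with Section 4.1 for shedders.

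The effect on VE ranges from none, if the vaccine prevents these cases equally, to a reading of 54% instead of 70%, with power of 82% instead of 93.5%. The upper end assumes that 15% of otherwise non-cases enter regardless of vaccine. The range of q is an assumption throughout, so bias is possible but not demonstrated. The sample size arithmetic is not in error. This is a cheap improvement to the one endpoint with a success criterion.

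**What to change.** - Reconcile Section 4.1, Section 4.3, Table 20 and the IV-fluid item in Section 11.2, so that it is clear which meaning of severe diarrhea applies to which endpoint.
- Keep the intervention limb in the primary case, but only where the IV fluids or early antibiotics are recorded as given for diarrhea.
- Pre-specify a sensitivity analysis of the primary endpoint using shedding with stool count, weight and temperature only. It may be placed in the statistical analysis plan.
- State in Section 11.4 whether the 58% attack rate was computed with the limb.

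The rules on when to treat are not touched. The cost is revised wording, one extra analysis, and the need to take the reason for each intervention from the recorded data.

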4.2. Dysentery (Amended: 23 July 2019)

For the purpose of the endpoint "Rate of shigellosis as defined by the CHIM expert working group occurring within a period starting with challenge visit and lasting until the end of the inpatient stay, in all subjects", dysentery is defined as follows:

• At least 2 loose stools with gross blood (hemoccult positive) in 24 hours AND [oral temperature ≥38.0°C OR ≥1 moderate constitutional/enteric symptom OR ≥2 episodes of vomiting in 24 hours]. In this case constitutional/enteric symptom are the following: nausea, abdominal pain, abdominal cramping, myalgia, arthralgia, malaise.

For the purpose of the endpoint "Rate of shigellosis, as defined by: severe diarrhea OR moderate diarrhea with fever or with one or more moderate constitutional/enteric symptoms OR dysentery", dysentery is defined as follows:

• At least 2 loose stools with gross blood (hemoccult positive) in 24 hours AND [≥1 reportable constitutional/enteric symptom]. In this case constitutional/enteric symptom are the following: headache, fatigue, arthralgia, malaise, myalgia, chills, nausea, abdominal cramping, abdominal pain, gas, anorexia, vomiting.

For the purpose of the endpoint "Rate of more severe shigellosis as defined by: severe or moderate diarrhea with fever or with one or more severe constitutional/enteric symptom OR dysentery [[≥ 2 loose stools with gross blood (hemoccult positive) in 24 hours] AND [oral temperature $\geq 38.0^{\circ}C$ $OR \geq 1$ severe constitutional/enteric symptom]].", dysentery is defined as follows:

• At least 2 loose stools with gross blood (hemoccult positive) in 24 hours] AND [oral temperature ≥38.0°C OR ≥1 severe constitutional/enteric symptom]. In this case constitutional/enteric symptom are the following: headache, fatigue, arthralgia, malaise, myalgia, chills, nausea, abdominal cramping, abdominal pain, gas, anorexia, vomiting.

For the purpose of the endpoints "Dysentery" and "Confirmed S. sonnei 53G shedding AND moderate or severe diarrhea OR dysentery OR presence of oral temperature ≥ 38.5°C OR presence of one or more severe intestinal symptoms (abdominal pain, cramping, nausea, vomiting, gas, and anorexia)", dysentery is defined as follows:

• A Grade 3, 4, or 5 stool with gross blood on at least 2 occasions within 24 hours and presence of constitutional/enteric symptoms. In this case, constitutional/enteric symptoms consist of headache, fatigue, arthralgia, malaise, myalgia, chills, nausea, abdominal cramping, abdominal pain, gas, anorexia, vomiting, and fever.

(Amended: 23 July 2019)

205626 (S SONNEI MONO GMMA SBVGH-003 [H03_03TP])
Protocol Amendment 6 Final

4.3. Shigellosis

For the primary and secondary objectives in the challenge phase of the study, the protocol primary case definition for shigellosis is:

• Shedding of *S. sonnei* 53G accompanied by moderate or severe diarrhea OR shedding with an oral temperature of ≥ 38.5 °C).

For the secondary objectives in the challenge phase of the study, 2 definitions of shigellosis are used:

- 1. CHIM working group case definition for shigellosis as defined by any one of the three following possible endpoints:
 - Severe diarrhea defined as [≥6 loose stools in 24 hours] OR [>800 grams loose stools in 24 hours]
 - Moderate diarrhea defined as [4-5 loose stools in 24 hours OR 400-800 grams loose stools in 24 hours] AND [oral temperature ≥38.0°C OR ≥1 moderate constitutional/enteric symptom OR ≥2 episodes of vomiting in 24 hours]
 - Dysentery defined as [≥2 loose stools with gross blood (hemoccult positive) in 24 hours] AND [oral temperature ≥38.0°C OR ≥1 moderate constitutional/enteric symptom OR ≥2 episodes of vomiting in 24 hours].
- 2. Shigellosis as defined by any one of the three following possible endpoints:
 - Severe diarrhea defined as [≥6 loose stools in 24 hours OR >800 grams loose stools in 24 hours]
 - Moderate diarrhea defined as [4-5 loose stools in 24 hours OR 400-800 grams loose stools in 24 hours] AND [oral temperature ≥38.0°C OR ≥1 moderate constitutional/enteric symptom].
 - Dysentery defined as [≥2 loose stools with gross blood (hemoccult positive) in 24 hours] AND [≥1 reportable constitutional/enteric symptom].

For the secondary objectives in the challenge phase of the study, more severe shigellosis is defined by any one of the two following possible endpoints:

- Moderate OR severe diarrhea [≥4 loose stools in 24 hours OR ≥400 grams loose stools in 24 hours] AND [oral temperature ≥38.0°C OR ≥1 severe constitutional/enteric symptom].
- Dysentery defined as [≥2 loose stools with gross blood (hemoccult positive) in 24 hours] AND [oral temperature ≥38.0°C OR ≥1 severe constitutional/enteric symptom]. (Amended: 23 July 2019)

205626 (S SONNEI MONO GMMA SBVGH-003 [H03_03TP])
Protocol Amendment 6 Final

5. STUDY COHORT

5.1. Number of subjects/center

Target enrolment is up to 72 eligible subjects (36 per treatment group). Refer to Sections 5.2 and 5.3 for eligibility criteria and to Section 11.4 for the determination of sample size.

Enrolment will take place in 4 overlapping cohorts of 18 subjects each to accommodate for the availability of beds required for the challenge phase of the study at the clinical site (see also Section 11.12.1). However, if for any reason, a cohort does not reach the planned 18 subjects, additional subjects can be added in the next cohorts. The maximum number of subjects must not be more than 20 (maximum number of beds in the clinic) in each cohort. The vaccination and challenge will be done per cohort.

5.2. Inclusion criteria

Deviations from inclusion criteria are not allowed because they can potentially jeopardize the scientific integrity, regulatory acceptability of the study or subject safety. Therefore, adherence to the criteria as specified in the protocol is essential.

All subjects must satisfy ALL the following criteria at study entry:

- Subjects who, in the opinion of the investigator, can and will comply with the requirements of the protocol (e.g. completion of the diary cards, return for follow-up visits).
- Written informed consent obtained from the subject prior to performing any study specific procedure.
- Individuals who, after the nature of the study has been explained to them, have shown adequate comprehension of the study procedures and knowledge of study.
- A male or female between, and including, 18 and 50 years of age at the time of the first vaccination.
- Healthy subjects as established by medical history and clinical examination before entering into the study.
- Seronegative for HIV, hepatitis B and C.
- Female subjects of non-childbearing potential may be enrolled in the study.
 - Non-childbearing potential is defined as pre-menarche, current bilateral tubal ligation or occlusion, hysterectomy, bilateral ovariectomy or post-menopause.

Please refer to the glossary of terms for the definition of menarche and menopause.

- Female subjects of childbearing potential may be enrolled in the study, if the subject:
 - Has practiced adequate contraception for 30 days prior to vaccination, and
 - Has a negative pregnancy test on the day of vaccination, and
 - Has agreed to continue adequate contraception during the entire study period.

Please refer to the glossary of terms for the definition of adequate contraception.

205626 (S SONNEI MONO GMMA SBVGH-003 [H03_03TP])
Protocol Amendment 6 Final

